The purpose of this randomized, triple-blinded, prospective, feasibility study is to compare postoperative analgesia provided by PIFB when performed with local anesthetic solution with or without perineural adjuvants in patients following cardiac surgery involving sternotomy. We hypothesize that the patients receiving PIFB with bupivacaine with epinephrine, clonidine, and dexamethasone will have lower dynamic pain over the first 24 hours compared to those receiving PIFB with just bupivacaine and epinephrine. The primary outcome will be the 24 hour area under the curve (AUC) pain scores, based on patient-reported dynamic NRS pain scores with incentive spirometer (IS) use measured at 6, 12, 18, and 24 hours after block placement in patients that are extubated. We set a minimally clinical important difference (MCID) to be 10% for AUC pain scores with IS use. Secondary outcomes will include patient-reported NRS pain scores at rest at 6, 12, 18, and 24 hours after block placement; cumulative 24 hour opioid consumption; time to first postoperative opioid administration after extubation; time to extubation; duration of ICU admission; incentive spirometry volumes at 6, 12, 18, and 24 hours after block placement;

nausea incidence; vomiting incidence; postoperative delirium incidence; and patient-reported NRS satisfaction with the analgesic regimen.

Risks to Subjects

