Patients randomized to the control arm will receive bilateral PIFB with a total of 60cc of 0.25% bupivacaine with 2.5mcg/cc epinephrine (1:400,000 dilution), and those in the experimental arm will receive bilateral PIFB with a total of 60cc of 0.25% bupivacaine with 2.5mcg/cc epinephrine (1:400,000 dilution), 1.67mcg/cc clonidine, and 0.1mg/cc preservative-free dexamethasone.

Patients will be monitored throughout block placement using standard ASA monitors including telemetry, heart rate, blood pressure, pulse oximetry, and end-tidal capnography. Following placement of bilateral PIFB, patients will be transported still intubated to the ICU with propofol infusion for sedation, as per institutional protocol for routine postoperative care.

As is our current practice, patients will be managed with ICU nursing-administered titrated boluses of IV fentanyl for analgesia before extubation based upon signs of nociception, including hypertension, tachypnea, facial grimace, and motor agitation. Patients will have as-needed doses of oxycodone and/or hydromorphone ordered for analgesia after extubation, unless they have a contraindication or allergy, in which case a suitable alternative at equianalgesic doses will be ordered.

Materials

Ultrasound guidance for imaging the relevant anatomy will be obtained using a linear ultrasound probe. All PIFB will be performed in a sterile manner, using sterile gloves, sterile ultrasound probe cover, sterile short-bevel block needle, and skin cleaning using an aseptic cleaning solution prior to placement. All products used are FDA-approved for the above-mentioned procedures, and an Investigational New Drug (IND) exemption has been obtained for use of the study medications used in this protocol under FDA IND165506.

Measurements

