The time of block placement will be documented as the zero hour time point for the purposes of measurements. As described above, to collect data for the primary outcome, research staff will elicit patient-reported NRS pain scores with use of incentive spirometry at 6, 12, 18, and 24 hours post block placement. If patients are not yet extubated at the 6 hour point, they will be excluded from the study as mentioned above. Research staff will also collect data for secondary outcome measures including, but not limited to: eliciting resting NRS pain scores at 6, 12, 18, and 24 hours after block placement; measuring incentive spirometry volumes in triplicate at 6, 12, 18, and 24 hours; measuring the time after extubation to first opioid administration; time to extubation; duration of ICU admission; calculating incidence of nausea and vomiting based on the administration of the antiemetics ondansetron, metoclopramide, prochlorperazine, and promethazine; assessing delirium based on bedside ICU nurse documentation using Confusion Assessment Method in the ICU (CAM-ICU) in the first 24 hours post block placement; and measuring patient-reported NRS satisfaction with the analgesic regimen at the 24 hour point (0 represents completely unsatisfied and 10 represents completely satisfied).

For the NRS pain scores and measurement of incentive spirometer volumes at each 6, 12, 18, and 24 hours interval, there is a grace period of 1 hour. This is to give the research staff/ ICU nurse the flexibility of completing these tasks.

The cumulative 24 hour opioid consumption will be abstracted from the EMR. All opioids will be converted to oral morphine milligram equivalents (OMME) to allow for appropriate comparison using a widely available dose conversion table. These metrics will be accessed, abstracted, de-identified, and analyzed by research personnel who are blinded to group allocation.

There will also be a 30-day post-block phone call follow-up for ongoing opioid use/last use, such as frequency and dosage, and pain levels in their day-to-day activities.

Statistical Analysis

Power Analysis

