We define a minimum clinically important difference (MCID) to be a 10% reduction in area under the curve for our primary outcome. Given that no current data exist on the anticipated duration of PIFB with perineural adjuvants at our institution, we have decided to recruit 10 patients per arm for a total of 20 patients in this feasibility trial. Based on prior studies involving the use of perineural adjuvants with long-acting local anesthetics, we have noted an average duration around 20 hours for peripheral blocks performed at other sites with bupivacaine containing perineural adjuvants epinephrine, clonidine, and dexamethasone. We have therefore chosen 24 hours as the final time point, with serial checks starting at 6 hours post block placement to represent clinically important pain trajectories for patients recovering from cardiac surgery with sternotomy.

Data Analysis

Demographic information will be collected as mentioned above and compared between the groups to verify that randomization balanced important baseline variables between the control and experimental groups. For the primary outcome of AUC pain scores with use of incentive spirometry for the first 24 hours post block placement, we will compare mean and standard deviations of the overall integrated area under the curve using the trapezoid rule. For secondary outcomes with continuous variables, such as intubation or ICU duration, t-tests and confidence intervals will be calculated. For continuous variables with serial measurements, repeated measure analysis of variance (RMANOVA) will be used. Further assistance with statistical analysis is being elicited from the Clinical and Translational Science Institute (CTSI), and this IRB protocol will be updated with further details after final review with a statistician.

Missing Data Points

Missing data points for the primary outcome will be imputed by a mixed effects modeling framework that allows us to use all available data points to tests hypotheses about differences between the two groups at each time point. Models will be implanted using the 'lme4' package in R statistical software.

Human Subjects Protection

Subject Recruitment Methods

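### Time to first opioid after extubation: no rule for patients who take none, and the only listed test that fits would leave them out if run on recorded times

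*Combined protocol and SAP*

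**What the plan says.** The Objectives list "time to first postoperative opioid administration after extubation" among the secondary outcomes, and Measurements repeats it as "measuring the time after extubation to first opioid administration". The clock therefore starts at extubation, whereas the other timed assessments count from block placement. Under Interventions, "Patients will have as-needed doses of oxycodone and/or hydromorphone ordered for analgesia after extubation", so a patient need not receive any.

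Data Analysis gives two methods for continuous secondary outcomes. One is repeated-measures ANOVA for serial measurements. The other is this sentence: "For secondary outcomes with continuous variables, such as intubation or ICU duration, t-tests and confidence intervals will be calculated". Time to first opioid is not named in either place.

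Three other statements come close to this outcome without settling it:
- Power Analysis: "We have therefore chosen 24 hours as the final time point, with serial checks starting at 6 hours post block placement".
- Measurements: "The cumulative 24 hour opioid consumption will be abstracted from the EMR". This window is stated for the cumulative dose only.
- Missing Data Points: "Missing data points for the primary outcome will be imputed by a mixed effects modeling framework". Secondary outcomes are not covered.

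The 30-day call asks about continuing and most recent opioid use, not first use. Data Analysis also says that statistical help is being sought and that more detail will follow a statistician's review.

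**The concern.** A patient who takes no opioid while observed is not a missing value. The event has not happened, and the time is known only to exceed the observed period. A t-test needs a number for each patient, so on recorded times it silently drops these patients, who are the clearest successes on this outcome. If the adjuvants work, there may be more of them in the experimental arm, and dropping them would pull the estimated difference toward zero.

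The window matters as well. The 24 h time point is a plausible end of observation, but the plan does not tie it to this outcome. Two analysts with the same records could choose different ends of observation and different values for non-users, and so report different results.

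**Working it through.** **Inputs from the documents.** There are 10 patients per arm, 10 × 2 = 20 in total (Power Analysis). That is a feasibility choice, with no alpha, power, SD or event rate behind it, so there is no calculation to reproduce. Patients still intubated at 6 h after the block are excluded (Selection Criteria, Measurements). If observation ends at 24 h after the block, every analysed patient is therefore followed for at least 24 − 6 = 18 h after extubation.

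**Assumptions, none from the documents.** Exponential times to first opioid, the medians and non-use rates shown, extubation uniform between 3 and 6 h, and two-sided alpha of 0.05.

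**Simplest case.** Every opioid taker has the first dose at 4 h. No control patient but 2 of 10 experimental patients take none. On recorded times the difference is 4 − 4 = 0 h. With everyone counted to 18 h it is 0.2 × (18 − 4) = 2.8 h.

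**Closed form, follow-up of 18 h for all, median m.**
- Share with no opioid: p = 2^(−18/m).
- Mean with everyone counted to 18 h (restricted mean): (m/ln 2)(1 − p).
- Mean of recorded times only: m/ln 2 − 18p/(1 − p).

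For m = 4 h, p = 0.044 and the two means are 5.52 h and 4.94 h. For m = 8 h, p = 0.210 and they are 9.12 h and 6.75 h. The difference is 3.60 h with everyone counted and 1.81 h on recorded times, so half is lost.

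**Simulation, 20,000 trials per row, 10 per arm.** Follow-up varies with extubation time. The all-patient difference caps times at 18 h after extubation (42 h or 66 h for the longer windows). Power is for a Student t-test on recorded times, a Welch test on capped times, and an asymptotic log-rank test.

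| Medians (h) | End after block | No opioid, control / exp. | Recorded only (h) | All patients (h) | Power: t / Welch / log-rank |
|---|---|---|---|---|---|
| 1 v 2 | 24 h | 0.0% / 0.1% | 1.42 | 1.43 | 25% / 22% / 31% |
| 2 v 4 | 24 h | 0.1% / 3.4% | 2.23 | 2.65 | 23% / 24% / 32% |
| 4 v 6 | 24 h | 3.4% / 10.5% | 1.30 | 2.07 | 9% / 12% / 15% |
| 4 v 8 | 24 h | 3.4% / 18.4% | 2.05 | 3.59 | 14% / 26% / 31% |
| 4 v 12 | 24 h | 3.6% / 32.4% | 2.85 | 5.63 | 21% / 52% / 59% |
| 4 v 8 | 48 h | 0.1% / 2.2% | 4.76 | 5.44 | 24% / 23% / 32% |
| 4 v 12 | 48 h | 0.1% / 8.1% | 7.73 | 10.01 | 46% / 53% / 62% |
| 4 v 8 | 72 h | 0.0% / 0.3% | 5.61 | 5.78 | 25% / 22% / not run |

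A separate run of 4 v 8 h to 24 h gave 13% v 25% power (t v Welch). In the 1 v 2 h row the gap of 25% to 22% is only Student against Welch; with Welch on both it is 22.0% v 21.9%.

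**Type I error.** With equal medians (4 v 4 h, 8 v 8 h) the differences were within 0.02 h of zero. Rejection rates were 5.0% for recorded times and 5.9% to 6.4% for the asymptotic log-rank test. The log-rank powers above are therefore slightly flattered, and an exact or permutation version is the safer choice.

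**Other non-use patterns.**
- Non-use 0% v 20%, same times among users (mean 5 h, SD 3): −0.02 h recorded v 2.58 h with everyone; power 5% v 15%.
- Non-use 10% in both arms, users at mean 4 v 7 h (SD 2): 2.98 h recorded v 2.69 h with everyone; power 84% v 35%. Nothing is understated here, and the capped mean is the noisier estimate.

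**Is a Welch interval for the capped mean safe?** Coverage was 93% to 95% in the 24 h rows with a treatment effect. It fell to about 69% to 90% when only 10% or 20% of one arm took no opioid and users' times were tight. For example, take 10% non-use in the experimental arm only, with users at mean 3 h and SD 1. The true difference is 0.1 × (18 − 3) = 1.5 h. With probability 0.9^10 = 35% the arm shows no non-user at all. The interval then has a half-width near 2.10 × √(2/10) = 0.94 h around roughly zero, and usually misses 1.5 h.

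**The case against.** The strongest reply is that the faulted analysis is inferred. The t-test sentence gives intubation and ICU duration as its examples, nothing says that non-users will be dropped, and the section is openly unfinished. A reader might infer that the plan has chosen to discard opioid-free patients. The documents do not support that: the outcome is under-specified rather than wrongly specified. What remains is that no other listed method fits and no rule covers these patients.

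Second, 24 h is a fair reading of the intended window, because the hypothesis, the cumulative opioid dose, the delirium assessment and the satisfaction score all use it. This also stands. But that clock runs from the block and this outcome's clock from extubation, and ICU duration and the 30-day call show that data collection does not stop at 24 h.

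Third, the larger losses need observation to stop at 24 h. If records are read until 48 h or 72 h, the 4 v 8 h case loses no power, and only 4 v 12 h at 48 h shows a modest loss. This is correct and limits the claim.

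Fourth, the size is wholly assumed. A reader might infer from the roughly 20 h block duration in Power Analysis that many experimental patients will be opioid-free at 24 h. That figure comes from blocks at other sites, and the same section says: "Given that no current data exist on the anticipated duration of PIFB with perineural adjuvants at our institution".

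Finally, cumulative 24 h opioid consumption keeps non-users, so the trial does not lose the information altogether.

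**Conclusion.** The point holds as a minor one. The plan leaves a time-to-event outcome without a stated end of observation, without handling for patients who have no event, and without a suitable method. The only listed test that fits would exclude those patients if run on recorded times.

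The understatement is conditional. It needs observation to end near 24 h and more opioid-free patients in the experimental arm. Under assumed medians of 4 v 8 h it is about 2.0 h against 3.6 h, with power about 13% against 25%. It shrinks to nothing with early first doses, is small with long observation, and is absent when non-use is equal in both arms. It would therefore be wrong to conclude that the plan is generally biased against the adjuvants. Nor was an excess of false positives seen for the recorded-times t-test.

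Every rate behind these figures is an assumption. This is one secondary outcome in a 20-patient feasibility trial, and power is low for most of the assumed effects by any method.

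**What to change.** When Data Analysis is updated, name this outcome and state that:
- observation ends 24 h after block placement, and patients with no opioid after extubation by then are censored at that time;
- the number of patients per arm with no opioid is reported;
- the arms are compared with Kaplan-Meier curves and a log-rank test, exact or by permutation given 10 per arm, in place of the t-test.

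A restricted mean difference to 18 h after extubation may be added as a descriptive estimate, since that span is fully observed for every analysed patient. Give it a permutation or other small-sample interval, and do not state that a Welch interval is adequate. The coverage of such alternatives was not checked here. When no non-user happens to be seen in an arm, any interval may be too narrow, which is another reason to show the counts beside it.

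The cost is wording. The analysed patients do not change, and 24 h opioid use is already taken from the medical record. The downsides are that the result applies only to the stated window and that power stays low.

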Exclusion: Patients with any contraindications to regional anesthesia, such as history of allergy to amide local anesthetics or any of the perineural adjuvants; existing neurologic deficit in the chest wall; remaining intubated at the six hour point after block placement; weight under 50kg; undergoing emergency surgical procedures or urgent return to the operating room; active endocarditis or mediastinitis; moderate to severe right ventricular function before or after cardiopulmonary bypass; reliance on mechanical circulatory support devices, such as intra-aortic balloon pump or Impella; reliance on extracorporeal membrane oxygenation; localized or systemic infection; chronic use of high dose opioid analgesics (defined as daily use greater than 30 oral morphine milligram equivalents (OMME) for over one month prior to surgery); as well as those who are pregnant, will be excluded from participation. Intraoperative opioids will be limited to fentanyl, therefore patients who receive any other opioids will be excluded. Additionally, any administration of ketamine, methadone, and dexmedetomidine during intraoperative and postoperative settings will exclude the subjects from the study. Furthermore, postoperative administration of tramadol, NSAIDs, muscle relaxants, and Haldol will exclude the subjects from the study. Any patients who refuse enrollment or withdraw their consent will also be excluded and any of their information already collected will be destroyed.

Setting

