Patients between 18 and 90 years of age, scheduled to undergo cardiac surgery involving sternotomy at Atrium Health Wake Forest Baptist will be screened for eligibility. These patients will be approached for enrollment by research staff either during their preoperative assessment clinic visit prior to their surgery date, or when admitted as inpatients and scheduled for surgery. During this visit, the study will be discussed in detail, and eligible participants will be offered the ability to ask any questions and sign consent forms at that time, or decide at a later time prior to surgery. Study staff will also review the surgical schedule and offer to call eligible participants to discuss the research study to determine their interest. At that time, if interest is shown, the consent will be emailed to them for review prior to their hospital admission to allow adequate time for consideration. Those subjects will then be seen on the morning of surgery to obtain a written informed consent. All patients will be provided with a signed copy of their written informed consent for their records.

Study Protocol

Baseline data collection

After time of consent, enrolled patients will be informed on the appropriate use of an incentive spirometer (IS), asked to rate their baseline verbal pain score both at rest and with use of an incentive spirometer (IS) on the eleven-point numerical rating scale (NRS: 0-10, where 0 represents no pain and 10 represents the worst imaginable pain). Maximum effort IS volumes will be measured in triplicate and averaged, and patient characteristics will be recorded, including age, gender, height, weight, BMI, ASA physical status classification score, surgeon, planned surgical procedure, as well as preoperative opioid use and doses.

Randomization

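### The analysis of incentive spirometry volume makes no use of the baseline volume that is collected, and the repeated-measures ANOVA for serial secondary outcomes has no stated rule for missed visits

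*Combined protocol and SAP*

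**What the plan says.** The Objectives list among the secondary outcomes "patient-reported NRS pain scores at rest at 6, 12, 18, and 24 hours after block placement", and IS volumes at the same four times. The Measurements section repeats this for spirometry: "measuring incentive spirometry volumes in triplicate at 6, 12, 18, and 24 hours".

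The Data Analysis section does not name these two outcomes, but they fall under its general rule: "For continuous variables with serial measurements, repeated measure analysis of variance (RMANOVA) will be used". It names no covariate and no treatment of a missed visit.

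Baseline values exist. Under Baseline data collection, "Maximum effort IS volumes will be measured in triplicate and averaged, and patient characteristics will be recorded"; pain at rest and with IS use is also scored then. The only use the analysis text gives to baseline information is that it be "compared between the groups to verify that randomization balanced important baseline variables".

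The Missing Data Points section describes a mixed-effects model in lme4 that uses all available data. It is introduced for the primary outcome. The text neither extends it to the secondary outcomes nor rules that out.

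Two features bear on how much could be missing. The exclusion list includes "remaining intubated at the six hour point after block placement", and Measurements confirms: "If patients are not yet extubated at the 6 hour point, they will be excluded from the study as mentioned above". For each pain score and IS volume, "there is a grace period of 1 hour".

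**The concern.** There are two separate gaps of unequal weight.

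The main one is the unused baseline. Lung volume differs between patients before any block is placed. If a patient's pre-operative IS volume predicts the post-operative one, leaving it out of the model keeps that between-patient variation in the error term. With 10 patients per arm there is little precision to spare, and the measurement has already been made. This holds even with complete data.

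The second is conditional. Classical RMANOVA needs all four visits from every patient. If it is run that way and a patient misses one visit, up to three observed values go with it. The comparison then also leans on a stronger missing-data assumption than the mixed model, which needs only missing at random. Because the plan is silent, two analysts could follow it faithfully and analyse different sets of patients.

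**Working it through.** **No planned figure to reproduce.** The sample size of 10 + 10 = 20 is a feasibility choice with no standard deviation, power or formula behind it, and it is not disputed here. The documents give no correlation and no missingness rate, so every such input below is an assumption.

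**1. Baseline IS volume as a covariate, no missed visits**

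Inputs: N = 20 (Power Analysis); r = correlation of baseline with a post-block value (assumed); ρ = correlation between visits (assumed).

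Single visit. The variance of the adjusted arm difference relative to the unadjusted one is (1 − r²) × (N − 3)/(N − 4) = (1 − r²) × 17/16. The second term is the expected price of estimating one slope.

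Average of the four visits. Replace r² by r² ÷ [(1 + 3ρ)/4]. The divisor is 0.625 at ρ = 0.5 and 0.775 at ρ = 0.7.

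| r | single visit | average, ρ = 0.5 | average, ρ = 0.7 |
|---|---|---|---|
| 0 | 1.06 | 1.06 | 1.06 |
| 0.3 | 0.97 | 0.91 | 0.94 |
| 0.5 | 0.80 | 0.64 | 0.72 |
| 0.7 | 0.54 | 0.23 | 0.39 |

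Worked entry: r = 0.7, ρ = 0.5 gives (1 − 0.49/0.625) × 1.0625 = 0.216 × 1.0625 = 0.23.

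Break-even, where adjustment neither gains nor loses variance: r = √(1/17) = 0.24 for a single visit; √(0.625/17) = 0.19 and √(0.775/17) = 0.21 for the average.

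Cost if r = 0. The interval width changes by √(17/16) × t(17)/t(18) = 1.031 × 1.004 = 1.035, so it is 3.5% wider. At r = 0.3, 0.5 and 0.7 the single-visit width ratio is 0.99, 0.90 and 0.74.

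**2. Missed visits, only if RMANOVA is run on complete cases**

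Let m be the missing rate per visit. Expected patients dropped out of 20, with independent misses: 20 × [1 − (1 − m)⁴] if all four visits are at risk, or 20 × [1 − (1 − m)³] if the 6-hour visit is always observed. The clustered row uses a beta-binomial with correlation 0.3. The standard error (SE) ratio compares complete cases with all observed visits, for the arm difference averaged over visits, with ρ = 0.5 and simulated missing patterns.

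| pattern | m = 2% | m = 5% | m = 10% |
|---|---|---|---|
| independent, four visits at risk | 1.6 lost, SE ×1.04 | 3.7, ×1.11 | 6.9, ×1.25 |
| independent, 6 h observed | 1.2, ×1.03 | 2.9, ×1.08 | 5.4, ×1.18 |
| clustered, 6 h observed | 0.9, ×1.02 | 2.2, ×1.06 | 4.2, ×1.12 |

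At m = 0 the averaged arm contrast is the same under both methods before any covariate is added: on one simulated complete data set, the mixed model and a t-test on patient means both gave t = 2.322.

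**3. Which contrasts to report**

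The Missing Data Points section aims at differences at each time point, and an effect that works by prolonging the block may appear late. Take an assumed difference of 1 SD at 18 and 24 hours only, with ρ = 0.5 and 10 per arm:

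- Four-visit average: difference 0.5, SE √(2 × 0.625/10) = 0.354, ratio 1.41.
- Mean of 18 and 24 hours: difference 1, SE √(2 × 0.75/10) = 0.387, ratio 2.58.

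A replacement model should therefore keep the arm-by-visit test and the single-visit differences alongside the average.

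**The case against.** **Adjustment is optional.** An unadjusted comparison of randomised arms is valid, the text does not forbid a covariate, and a reader could even count the baseline reading as one of the serial measurements. Below a correlation of about 0.2 adjustment costs precision. All of that stands. It makes this an improvement in efficiency and clarity, not the correction of an invalid analysis. The most it can cost is small, while the gain at moderate correlation is not.

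**Baseline resting NRS is collected too.** True, and the plan could say whether it is used. It is not proposed as a covariate here: a pain score taken before there is a surgical wound need not track pain after it, whereas IS volume is the same breathing measure before and after. That is a judgement, since the documents give neither correlation.

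**Missed visits should be rare.** These are inpatients followed for 24 hours, extubated by 6 hours, with an hour's leeway per visit. A reader might infer that the plan specifies a complete-case analysis and will lose a large share of its 20 patients. The documents do not support that: they never say incomplete patients are dropped, they give no missingness rate, and they do not exclude using the mixed model here. The 10% column above is illustrative only. Patients removed for disallowed drugs are recovered by neither method.

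**The section is declared provisional.** The plan promises an update after review with a statistician. That does not fill the gap, but it makes this the right moment to do so.

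**Conclusion.** The point holds and is minor. The plan collects a baseline IS volume and names no use for it in the IS-volume analysis. Using it would multiply the single-visit variance by about 0.97, 0.80 or 0.54 at assumed correlations of 0.3, 0.5 or 0.7, with break-even near 0.24. For the visit-averaged contrast the factor at r = 0.7 is 0.23 to 0.39, for between-visit correlations of 0.5 to 0.7. The downside is one degree of freedom and an interval about 3.5% wider if baseline is uninformative.

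The missed-visit gap is real as an unstated rule. Its consequence needs both a complete-case RMANOVA and at least one missed visit; with none missed, nothing is lost.

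A reader might also infer a threat to the main result. There is none: the effect is confined to resting NRS and IS volume, and the primary AUC is unaffected.

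**What to change.** In the Data Analysis section, replace the RMANOVA sentence with:

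> Resting NRS and IS volume will each be analysed with a linear mixed model (lme4) with arm, visit, arm × visit and a patient random intercept, using all observed visits under missing at random, with Kenward-Roger degrees of freedom. The arm-by-visit test, and the arm differences at each visit and averaged over visits, will be reported with 95% confidence intervals. The IS-volume model includes baseline IS volume as a covariate. The number of missed visits is reported by arm and visit.

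This is a change of wording only. It needs no new data and uses software the plan already names, plus an add-on for the degrees of freedom. A random intercept carries the same compound-symmetry assumption as classical RMANOVA, so nothing is given up on the covariance structure.

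### No rule carries imputation uncertainty into the primary AUC; if missing scores are filled in once from the mixed model, its SD and standard error are too small

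*Combined protocol and SAP*

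**What the plan says.** Under Measurements, "research staff will elicit patient-reported NRS pain scores with use of incentive spirometry at 6, 12, 18, and 24 hours post block placement". For the primary outcome, the Data Analysis section says "we will compare mean and standard deviations of the overall integrated area under the curve using the trapezoid rule". It names no test and no confidence interval for this outcome; t-tests and confidence intervals are named only for continuous secondary outcomes.

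The Missing Data Points section reads "Missing data points for the primary outcome will be imputed by a mixed effects modeling framework", and the sentence continues "that allows us to use all available data points to tests hypotheses about differences between the two groups at each time point". It ends with "Models will be implanted using the 'lme4' package in R statistical software".

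The plan does not say whether imputation is single or multiple, how many imputations there are, how results are combined, or what is assumed about why scores are missing. On size, the Power Analysis section says "we have decided to recruit 10 patients per arm for a total of 20 patients in this feasibility trial". The Data Analysis section adds that further detail will follow after review with a statistician, without mentioning missing data.

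**The concern.** A trapezoid AUC for one patient needs all four scores, and imputation is the only remedy the plan gives for a gap. An analyst who follows the text would replace each missing score with a prediction from the fitted model, compute the AUC, and take means and SDs.

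A prediction has no residual noise and is pulled towards the mean of the patient's own arm at that visit. Completed AUCs therefore vary less than real ones. At the same time, the true sampling error of the arm difference grows, because fewer scores were observed. An SD or standard error computed from the completed AUCs misses both effects.

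The clause about using all available data does not settle the matter. It describes a direct model analysis, which needs no filled-in scores, but it is aimed at differences at each time point and gives no model-based estimate for the AUC. The text thus allows two procedures with different error properties and does not choose between them. What is at stake is the stated precision of the only primary outcome.

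**Working it through.** **The plan's own figures.** None bears on this point. The 10 per arm is a decision, not the result of a formula, and no SD, control mean, correlation or missing rate is given.

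**Inputs from the documents.** 10 patients per arm; scores at 6, 12, 18 and 24 h; trapezoid AUC. With 6 h spacing, AUC = 3(y6 + y12) + 3(y12 + y18) + 3(y18 + y24) = 3·y6 + 6·y12 + 6·y18 + 3·y24. There are 20 × 4 = 80 planned scores, so 5%, 10%, 20% and 30% missing means 4, 8, 16 and 24 scores.

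**Assumptions.** Correlation ρ between a patient's scores of 0.3, 0.5 or 0.7, equal for all pairs of visits; score SD 2 (it cancels from all ratios below); no true arm difference; each score missing independently with the same probability; mixed model with arm-by-visit means and a random patient intercept.

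**Why a prediction is too quiet.** If one score is missing and three are observed, the predicted deviation is ρ/(1 + 2ρ) times the sum of the three observed deviations (variance parameters taken as known). Its variance is 3ρ²/(1 + 2ρ) of that of a real score:
- ρ = 0.3: 0.27/1.6 = 0.17
- ρ = 0.5: 0.75/2.0 = 0.38
- ρ = 0.7: 1.47/2.4 = 0.61

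The loss is large at low correlation and moderate at high correlation.

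**Anchor for the simulation.** With complete data, Var(AUC) = 4[(1 − ρ)·90 + ρ·324], where 90 = 3² + 6² + 6² + 3² and 324 = 18². For ρ = 0.3 this is 640.8, so the SD is 25.3 and the standard error of the difference is 25.3 × √(2/10) = 11.3. The simulated value at 5% missing was 11.44, which agrees.

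**Simulation, about 3,000 runs per setting.** Gaps were filled once with the model prediction and the AUCs then treated as observed. The naive SE is the one computed from those AUCs; the true SE is the actual spread of the estimated difference. Type I error is for a nominal 5% t-test on 18 degrees of freedom, which is an added assumption. The last column takes the AUC contrast from the model instead, also referred to 18 degrees of freedom.

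| ρ | Missing | AUC SD / complete-data SD | Naive SE / true SE | Type I, filled in | Type I, model contrast |
|---|---|---|---|---|---|
| 0.3 | 5% | 0.988 | 0.976 | 5.6% | 4.7% |
| 0.3 | 10% | 0.973 | 0.936 | 6.9% | 4.7% |
| 0.3 | 20% | 0.941 | 0.879 | 8.8% | 4.6% |
| 0.3 | 30% | 0.906 | 0.831 | 11.7% | 4.4% |
| 0.5 | 5% | 0.993 | 0.999 | 5.0% | 4.5% |
| 0.5 | 10% | 0.984 | 0.969 | 6.1% | 4.9% |
| 0.5 | 20% | 0.963 | 0.933 | 7.0% | 4.6% |
| 0.5 | 30% | 0.935 | 0.877 | 9.4% | 5.4% |
| 0.7 | 5% | 0.996 | 1.005 | 5.1% | 5.0% |
| 0.7 | 10% | 0.992 | 0.985 | 5.5% | 4.9% |
| 0.7 | 20% | 0.980 | 0.987 | 5.3% | 4.4% |
| 0.7 | 30% | 0.964 | 0.937 | 7.5% | 4.9% |

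Complete data gave 4.0% to 5.4%. The model's own standard error was 0.99 to 1.03 of the true one.

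**Repeat.** A second simulation of the same size gave SE ratios of 0.95–1.00, 0.88–0.96 and 0.80–0.93 at 10%, 20% and 30% missing, and type I error of 5.4–6.2%, 5.6–9.1% and 7.1–13.0%; the model contrast stayed at 4.5–5.3%. The headline ranges are rounded from this repeat. Monte Carlo error is about √(0.05 × 0.95/3000) = 0.4 points on a 5% error rate and about 1/√6000 = 1.3% on an SE ratio. That is roughly the scale on which the two simulations differ (for example 0.936 against 0.95 at 10% missing, and 0.987 against 0.96 at 20%).

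**The case against.** The strongest reply is that the plan does not say what the literal reading supposes. A reader might infer that it commits to single imputation and to treating the completed AUCs as observed. No sentence says so, and the same sentence can be read as a direct likelihood analysis loosely called imputation, under which the simulation shows no understatement. This stands: the fault is conditional. It does not remove the point, because that analysis is described only for each time point.

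A reader might also infer that the primary confidence interval is too narrow and the false-positive rate inflated. The plan specifies neither an interval nor a test for the primary outcome, so the type I figures illustrate what a t-test would do. Nor does it follow that only imputed values can feed the AUC comparison: the AUC is a weighted sum of visit scores, so its mean difference can be read from the fitted model.

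The amount missing may be small. Scores are collected in hospital over 24 hours with a one-hour grace period, and one obvious source of gaps is removed: "If patients are not yet extubated at the 6 hour point, they will be excluded from the study as mentioned above". At 5% missing, or at correlation 0.7 with up to 20% missing, the tabulated error rate stays between 5.0% and 5.6%, so it would be wrong to say that it rises with every missed visit. Against this, 10% is only eight scores, patients are also being assessed for delirium, and the sponsor foresaw gaps by writing the section.

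Finally, concern about carrying a small SD into a later trial has little weight. With 18 degrees of freedom the pooled SD has a relative sampling error of about 1/√36 = 17%, against a shrinkage of at most 9% in the table, and the plan does not say that the SD will be used in that way.

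**Conclusion.** The point holds as a conditional fault of specification. The plan imputes primary scores and compares AUC means and SDs, but gives no rule for carrying imputation uncertainty into either. If gaps are filled in once with predictions, the standard error of the arm difference is understated by about 0–5% at 10% missing (6% in one tabulated setting), 4–12% at 20% (as little as 1% in one setting) and 7–20% at 30%. A t-test, if used, would run at about 5–6%, 6–9% and 7–13% (6.9% at most in the table at 10% missing). Near 5% missing the effect is negligible.

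These sizes rest on assumed correlations of 0.3 to 0.7, equal correlation between visits, and scores missing purely by chance. The documents give neither a correlation nor a missing rate. They do not support saying that the primary error bars will be too narrow, only that the text permits it. The matter deserves correction because a sound method uses the same model and costs almost nothing.

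**What to change.** Replace the imputation sentence with a statement that:

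- a mixed model with arm, visit, their interaction and a random patient intercept is fitted to all observed scores, without filling in any;
- the primary result is the arm difference in AUC, formed from the visit-specific differences with weights 3, 6, 6 and 3 over 6 to 24 h, with its standard error and 95% confidence interval taken from that model using small-sample degrees of freedom such as Kenward-Roger;
- scores are assumed missing at random, and the number missing is reported by arm and visit.

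Multiple imputation is an acceptable alternative if the AUC is computed in each completed data set and the difference is pooled by Rubin's rules.

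Report the descriptive AUC SD from patients with all four scores observed, with their number, and not from singly imputed AUCs.

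The cost is a few sentences in the plan, a few lines of code and a slightly wider interval. The complete-case SD may rest on few patients: with scores missing independently, about 20 × 0.9⁴ = 13 patients are complete at 10% missing, and 20 × 0.8⁴ = 8 at 20%. It should therefore serve as description only. The statistical update that the Data Analysis section already announces is the natural place for the change.
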